- b. The research could not practically be conducted without the access to and use of the PHI. Critically ill patients receiving care from BMT are eligible for multiple studies, both interventional and observational. This patient population is also understandably under a great deal of stress and the BMT repository has been created to minimize multiple requests for study participation, specifically those involving collection of samples collected by non-invasive means, such as urine.

5. Statistical Analysis Plan: We plan to enroll at least 100 subjects, 30 of whom will need to develop AKI by the KDIGO serum creatinine criteria (50% rise over baseline or a 0.3 mg/dl rise over baseline within 48 hours). If we have not enrolled at least 30 participants with AKI after a 100 participant total enrollment, we will continue to enroll up to another 100 participants to achieve a total of 30 AKI participants. Our current data from the NINJA project show that 15% of exposed participants develop AKI. For hypothesis 1, we will determine the sensitivity, specificity, positive predictive value and negative predictive value of urine NGAL to detect NTMx-AKI. Our goal is to achieve a NPV of >98% using an uNGAL concentration of <50 ng/ml to rule out serum creatinine based AKI development. For hypothesis 2, we will also assess sensitivity, specificity, PPV and NPV for the POC “low-risk” test to predict a clinical lab based NGAL level of <50 ng/ml.

Sample size estimates: With an assumption that 70 participants will not develop AKI in the first 7 days, we will have 490 samples for comparative analysis if we are able to stop at 100

participants. If we need to enroll 200 participants to achieve enroll 30 AKI participants, we would have 1190 samples (170x 7 days) for participants without AKI. Sample size analysis for non-inferiority (of NGAL to serum creatinine, of POC NGAL to clinical lab NGAL) reveals that we need 143 samples to be confident that we will not see a >2% discordance rate between the reference and test data set with a power of 0.8 and an alpha of 0.05. Clearly, we will have enough samples in the dataset. If we analyze the data on a per participant basis, again we will have enough participants if we enroll 200 total. At the minimum of 100 participants, our power is 0.67.

6. Security

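### Seven daily samples per child are counted one for one against a 143-sample requirement, and no method allows for correlation within a child

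*Combined protocol and SAP*

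**What the plan says.** Section 2 (Hypothesis 1, Methods) has one urine sample taken per day for seven days from each participant. The sample size paragraph of Section 5 turns this into counts:

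- At 100 enrolled: "With an assumption that 70 participants will not develop AKI in the first 7 days", and then "we will have 490 samples for comparative analysis if we are able to stop at 100".
- At 200 enrolled: "we would have 1190 samples (170x 7 days) for participants without AKI".
- The requirement, at power 0.8 and alpha 0.05: "we need 143 samples to be confident that we will not see a >2% discordance rate".
- The conclusion: "Clearly, we will have enough samples in the dataset".

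The participant as unit follows as an alternative: "If we analyze the data on a per participant basis, again we will have enough participants if we enroll 200 total", and "At the minimum of 100 participants, our power is 0.67".

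Section 5 lists sensitivity, specificity, PPV and NPV for both hypotheses. It names no interval, test or model, no allowance for several samples per child, and no rule for reducing seven results to one per child.

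**The concern.** The plan's argument is that 490 or 1190 is far more than 143. That is valid only if the seven samples from one child carry as much information as seven samples from seven children. A child whose uNGAL reads high on one day without AKI, or whose urine makes the point-of-care (POC) test misread, will probably do so again on other days.

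Two things could suffer. The first is inference: ordinary binomial intervals on sample counts would be too narrow, and a discordance below 2% would be claimed too often. The purpose is to replace daily serum creatinine, so unwarranted confidence in agreement is the costly error. The second is sufficiency: the effective number of samples might fall below 143.

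**Working it through.** **Inputs.** From Section 5: 70 and 170 children without AKI, the 143-sample requirement, the 2% limit, power 0.8, alpha 0.05, power 0.67 at 100 participants, and AKI in 15% of exposed participants. From Section 2: seven samples per child. From Section 1: 35 AKI episodes per 200 exposed patients, or 17.5%. The ICC is not in the documents, so every value below is an assumption.

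**The plan's own figures.** 70 x 7 = 490 and 170 x 7 = 1190 reproduce. The 143 cannot be checked, because the true discordance assumed behind it is not stated. With one-sided alpha 0.05 and power 0.8, three normal-approximation formulas return 143, each at a different true discordance p:

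- (za+zb)^2 p(1-p)/0.02^2: p about 0.93%
- (za+zb)^2 p(1-p)/(0.02-p)^2: p about 0.51%
- (za sqrt(0.02 x 0.98) + zb sqrt(p(1-p)))^2/(0.02-p)^2: p about 0.01%

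Taking 143 at power 0.80 as given, power at n = 100 is Phi((1.645+0.842) x sqrt(100/143) - 1.645) = 0.668. This matches the stated 0.67, with each of the 100 participants counted once.

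**Sufficiency.** Effective sample size = samples/(1 + 6 x ICC).

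- 490 samples: 222.7 at ICC 0.2, 122.5 at 0.5, 70 at 1. Break-even with 143 is (490/143 - 1)/6 = 0.40.
- 1190 samples: 540.9, 297.5 and 170 at the same ICCs, so never below 143.

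The break-even ICC rises with enrolment and reaches 1 at 143 children without AKI.

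Stopping at 100 needs at least 30 AKI cases in the first 100. The binomial probability is about 0.0001 at 15% and 0.0015 at 17.5%.

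**Inference.** Beta-binomial simulation with seven samples per child, true discordance 2% and 40,000 replicates. The naive exact one-sided 5% test claims less than 2% when the exact upper 95% bound, with all samples treated as independent, lies below 2%. Coverage is for naive exact two-sided 95% intervals.

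| Assumed ICC | False claim, 70 children | False claim, 170 children | Coverage, 70 | Coverage, 170 |
|---|---|---|---|---|
| 0 | 3.2% | 3.5% | 96.8% | 96.1% |
| 0.05 | 4.9% | 5.9% | 94.0% | 93.0% |
| 0.2 | 11.4% | 11.6% | 85.3% | 83.7% |
| 0.5 | 21.2% | 20.2% | 70.1% | 69.3% |

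More children do not help, because the factor 1 + 6 x ICC depends on samples per child and not on the number of children.

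**What the 2% refers to.** In children without AKI, a uNGAL result that disagrees with creatinine is a false positive, so these rows concern specificity. For POC against laboratory NGAL, all 100 or 200 children can contribute. False-claim rates there are 10.8% and 13.4% at ICC 0.2, and 19.9% and 21.5% at ICC 0.5.

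**The case against.** The strongest reply is that the plan does consider the participant as the unit directly after the quoted sentence, says 200 is enough and discloses power of only 0.67 at 100. This stands in part. It removes any suggestion that the issue was overlooked, and at 200 enrolled the comparison with 143 holds even at ICC 1. But the wording is conditional and no unit is chosen, so the sample-level route remains open with no method attached.

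Second, the plan names no interval or test, and its NPV above 98% is called a goal, so overconfidence arises only if a naive sample-level analysis is chosen. That is correct, and the point is worded accordingly.

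Third, the size rests on an ICC that nobody has given. Also correct: at 0.05 the false-claim rate is close to the nominal 5%, and the 20-21% figures need an ICC of 0.5, which nothing in the documents establishes.

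A reader might also infer two stronger things. One is that the trial has too few samples. The documents do not support this: "Our current data from the NINJA project show that 15% of exposed participants develop AKI", which makes a stop at 100 very unlikely, and 170 exceeds 143. The other is that these false-claim rates apply to the NPV goal. They do not: the 70 and 170 are children without AKI, whose samples cannot be false negatives, so the calculation says nothing direct about NPV.

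**Conclusion.** The concern holds in a limited form. The sufficiency argument treats correlated samples as independent, and neither the unit of analysis nor a method for clustered samples is pre-specified. If ordinary binomial methods are applied to samples, intervals are too narrow at any enrolment whenever the ICC is above zero. The excess is slight at an ICC of 0.05. It is material at 0.2, where the false-claim rate is about twice the nominal level and 95% intervals cover about 83-85%, and large at 0.5 (about four times; 69-71%). These sizes assume a beta-binomial model, seven samples from every child and a true discordance of exactly 2%.

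Sufficiency is a secondary matter, confined to a stop near 100 with an ICC above about 0.40. That 170 exceeds 143 is only a comparison with the plan's own figure; it does not establish 80% power for a clustered method, because the true discordance behind 143 is unknown. This should be fixed before analysis, but it does not call the design into question.

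**What to change.** 1. State the unit of analysis for each hypothesis. If it is the participant, say how seven results become one.
2. For every sample-level sensitivity, specificity, PPV, NPV and discordance rate, pre-specify intervals that account for clustering by participant. Discordant results may be few or absent, so choose a method that remains valid at few or zero events, and check its false-claim rate and coverage by simulation over a range of ICCs.
3. Replace the sentence quoted above with the effective sample size, samples/(1 + 6 x ICC), and the power of the chosen method over a range of ICCs at 100 and 200 participants. State the true discordance assumed behind 143.

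The cost is a few sentences in the plan, a short simulation and slightly more analysis code, with no new participants or samples. The downside is wider intervals and less favourable stated power.

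### The stated power of 0.67 at 100 participants, and the claim that 200 are enough, are not supported by the inputs given; on a total-discordance reading the 0.67 cannot be reached

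*Combined protocol and SAP*

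**What the plan says.** The figures are in Section 5 (Statistical Analysis Plan), under the sample size estimates of the combined protocol and SAP.

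- The framework is given as "Sample size analysis for non-inferiority (of NGAL to serum creatinine, of POC NGAL to clinical lab NGAL").
- The requirement is "we need 143 samples to be confident that we will not see a >2% discordance rate" between reference and test, "with a power of 0.8 and an alpha of 0.05".
- The per-participant case is introduced by "If we analyze the data on a per participant basis", and the plan then says "again we will have enough participants if we enroll 200 total".
- For the lower enrolment it says "At the minimum of 100 participants, our power is 0.67".
- On event rate: "Our current data from the NINJA project show that 15% of exposed participants develop AKI". Enrolment stops at 100 only if 30 AKI cases have been reached; otherwise it may continue for up to another 100.

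The section names no test and no sidedness, gives no assumed true discordance rate, and does not say whether discordance is total disagreement or a net difference between paired results.

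**The concern.** With a 2% limit and 100 participants, only two discordant participants are expected at the limit itself (100 × 0.02 = 2). Observing none is then weak evidence that the rate is below 2%, so a power of two thirds looks too high. The same doubt applies to 200, where four are expected.

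The central hypothesis is that daily urine NGAL can replace daily serum creatinine. A reader may take Section 5 as assurance that a 2% bound can be shown per child with 200 children, and with fair probability with 100. If that assurance is unfounded, perfect agreement in 100 children could be presented as meeting a bound it does not meet, and one or two discordances in 200 could leave the target unmet despite a sample called sufficient.

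**Working it through.** **Inputs from Section 5:** limit 2%, alpha 0.05, power 0.8, required number 143, enrolment 100 or 200, AKI rate 15%. **Assumptions, because the documents give none:** true discordance rates of 0.1% to 2%. Tests are one-sided, since that is what reproduces the plan's figure.

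**1. The plan's 0.67.** Normal scaling from 143 gives power(n) = Φ[(1.645 + 0.842)·√(n/143) − 1.645]. At n = 100 this is 0.668, so 0.67 is reproduced. With two-sided alpha (1.960 for 1.645) it is 0.649.

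**2. The plan's 143.**
- Smallest n at which zero discordances excludes 2%, exact one-sided: ln 0.05 / ln 0.98 = 148.3, so 149. At 143, 0.98^143 = 0.056 and the exact upper limit is 2.07%, a narrow miss; a score test would pass (p = 0.044).
- Paired normal approximation with a 2% margin: n = (1.645 + 0.842)² × d / 0.02², where d is total discordance. Setting n = 143 requires d of about 0.93%.

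So 143 appears only after back-solving for a rate that the plan does not state.

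**3. Total discordance, null hypothesis rate ≥ 2%, n = 100.**
- Best possible result, 0/100: exact p = 0.98^100 = 0.133; exact upper limit 1 − 0.05^(1/100) = 2.95%.
- Score test: z = −0.02/√(0.02 × 0.98/100) = −1.43, p = 0.077.
- Neither rejects, so power is 0 by both.
- Ceiling for any level-0.05 test, allowing randomisation and a true rate of zero: 0.05/0.1326 = 0.38.

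**4. Total discordance, n = 200.**
- 0/200: exact p = 0.98^200 = 0.018, limit 1.49%; score p = 0.022. Passes.
- 1/200: exact p = 0.089, limit 2.35%; score z = −1.515, p = 0.065. Fails.
- Power is therefore (1 − p)^200: 82%, 37% and 13% at assumed true rates of 0.1%, 0.5% and 1%.
- 80% power needs p ≤ 1 − 0.8^(1/200) = 0.11%.
- At an assumed 0.5%, exact power first reaches 80% at n = 386 (three discordances allowed; power 0.87), above the maximum of 200.

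**5. Net paired difference, 2% margin, score test.**
- n = 100: no discordance gives p = 0.077 (fails); 0 unfavourable and 1 favourable gives p = 0.040 (passes).
- n = 200: 1 unfavourable and 1 favourable gives p = 0.037 (passes).

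| Assumed total discordance, split equally | Power at 100 | Power at 200 |
|---|---|---|
| 0.5% | 0.17 | 0.73 |
| 1% | 0.24 | 0.62 |
| 2% | 0.26 | 0.48 |

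Power of 0.67 at 100 is reached with about 1.1% discordance, all of it favourable; at 2%, all favourable, it is 0.87.

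**6. Which enrolment matters.** At 15% AKI, the probability of at least 30 cases among 100 (binomial) is about 0.0001. Stopping at 100 is very unlikely, so the statement about 200 carries more weight.

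**The case against.** The strongest reply is that the sentence is framed as non-inferiority, which ordinarily means a margin on a difference, and that the word total does not appear. On a net paired reading, 0.67 at 100 is attainable in principle and 200 does not require zero discordances. This stands, and it means that replacement wording cannot be imposed before the hypothesis is known. It does not rescue the figures as printed: balanced discordance gives at most 0.26 at 100 among the rates tried, and less than 0.8 at 200 for all three.

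A second reply is that other tests are more lenient. A Wald limit (1.3%) or a Jeffreys limit (1.94%) passes 1/200, and a Jeffreys limit (1.9%) passes 0/100. True, but on total discordance those rules have actual error rates of 8.9% and 13.3%, not 5%.

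A third is that little depends on this. The per-participant analysis is conditional, enrolment follows the AKI count, and the listed analyses are sensitivity, specificity and predictive values, with no pass/fail discordance test. That limits the consequence, but the plan still states a power and an adequacy claim that it does not support.

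A reader might also infer that the study's sample count is inadequate. This calculation does not show that. If samples are independent, 490 allows 4 discordances (power 0.90 at an assumed 0.5%) and 1190 allows 15 (0.85 at an assumed 1%).

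**Conclusion.** The concern holds as one of unsupported stated power. A reader might infer an arithmetic slip; there is none, because 0.67 follows from 143. A reader might also infer that power at 100 is zero whatever is meant; that is true of the total-discordance reading only, which is the closer one to the words discordance rate.

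On that reading, 0.67 is unattainable at 100, and the claim for 200 holds only if no discordance is observed. On the net paired reading, 0.67 depends on an unstated assumption of about 1.1% discordance, all favourable, and the claim for 200 falls short of 80% power at the balanced rates examined. On either reading 143 lacks a stated basis. That normal scaling was the method used is an inference from the match at 0.668; the plan names none.

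The powers rest on assumed true rates. The failure of 0/100 to exclude 2% does not; it needs only the 2% limit and one-sided alpha 0.05, and a two-sided test would be stricter. This should be fixed, but it does not threaten the conduct of the study.

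**What to change.** State in Section 5 whether the hypothesis concerns total disagreement or a net paired difference, and give the test, the sidedness and the assumed true discordance with its basis. Then replace 143, 0.67 and the unqualified claim for 200 with figures recomputed by an exact or score method for that hypothesis.

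- If total disagreement is meant: remove 0.67; say that 100 participants can at best exclude about 3% (one-sided 95%, no discordance); and say that 200 excludes 2% only with no discordance (limit 1.49%), with 80% power only if the true rate is about 0.11% or less.
- If a net paired difference is meant: report the paired power at 100 and at 200 under the stated assumption about the amount and direction of discordance.

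The cost is SAP wording and one recalculation, with no extra patients or samples. The drawback is that the stated figures become less favourable.
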